## **1.4 NONCLINICAL EXPERIENCE WITH RANIBIZUMAB**

### **1.4.1 Nonclinical Pharmacokinetics**

The pharmacokinetics of ranibizumab have been investigated in rabbits and cynomolgus monkeys following intravitreal and intravenous administration. In both species, following intravitreal administration, ranibizumab was cleared from the vitreous humor with a half-life of 2–3 days. Following single intravitreal administration to cynomolgus monkeys, retinal concentrations of ranibizumab were approximately one-third of vitreous concentrations and declined in parallel with vitreous

concentrations. In humans, the intravitreal half-life of ranibizumab is estimated to be 7-8 days. Repeated intravitreal injections of ranibizumab can lead to detectable antibodies in serum in rabbits and cynomolgus monkeys.

#### **1.4.2 Nonclinical Toxicology**

A series of nonclinical studies of ranibizumab administered by intravitreal injection to cynomolgus monkeys have been performed (details regarding study design and results can be found in the Investigator Brochure).

#### **1.4.3 Nonclinical Data Supporting the Anti-Edema Activity of Ranibizumab**

In Studies 01-401E-1757 and 01-401G-1757, the effect of ranibizumab on vascular leakage was explored using a modified Miles assay in the guinea pig. Ranibizumab demonstrated a concentration-dependent effect of blunting the vascular permeability induced by VEGF. These results are consistent with the decrease in retinal vascular permeability as observed on optical coherence tomography (OCT) and fluorescein angiography in AMD and diabetic macular edema studies and further support the rationale for the use of ranibizumab in CRVO and BRVO, in which vascular permeability plays a significant role in the pathology

### **1.5 CLINICAL EXPERIENCE WITH RANIBIZUMAB**

Ranibizumab has been or is being studied in more than 5000 subjects with neovascular AMD in a number of Phase I, I/II, II, III, and IIIb clinical trials. Ranibizumab is contraindicated in patients with ocular or periocular infections and in those with known hypersensitivity to ranibizumab or any of the excipients in ranibizumab. Intravitreal injections, including those with ranibizumab, have been associated with endophthalmitis and retinal detachment. Proper aseptic injection technique should always be used when administering ranibizumab. Increases in IOP have been noted within 60 minutes of intravitreal injection with ranibizumab. Therefore, IOP as well as perfusion of the optic nerve head should be monitored and

managed appropriately. Serious adverse events related to the injection procedure have occurred in <0.1% of intravitreal injections include endophthalmitis, rhegmatogenous retinal detachment, and iatrogenic traumatic cataract. Other serious ocular adverse events observed among ranibizumab-treated subjects and occurring in <2% of subjects included intraocular inflammation and increased IOP. The most common adverse reactions (reported  $\geq$  6% higher in ranibizumab-treated subjects than control subjects) were conjunctival hemorrhage, eye pain, vitreous floaters, increased IOP, and intraocular inflammation.,

Although there was a low rate (<4%) of arterial thromboembolic events (ATEs) observed in the ranibizumab clinical trials there is a potential risk of ATEs following intravitreal use of inhibitors of VEGF. The rate of ATEs in three studies (FVF2598g, FVF2587g, and FVF3192g) in the first year was 1.9% of subjects in the combined group of subjects treated with 0.3 mg or 0.5 mg ranibizumab compared with 1.1% of subjects in the control arms of the studies. In the second year of Study FVF2598g and FVF2587g, the rate of ATEs was 2.6% of subjects in the combined group of those treated with 0.3 mg or 0.5 mg ranibizumab compared with 2.9% of subjects in the control arm. The most common non-ocular adverse reactions observed in  $\geq$  15% of ranibizumab-treated subjects that occurred more frequently than in control subjects included, nasopharyngitis, headache, and upper respiratory tract infection.

The Sailor study (FVF3689g) evaluated the safety of intravitreal ranibizumab in a large population of subjects with CNV secondary to AMD. Subjects in Cohort 1 (N=2378) were randomized (1:1) to receive ranibizumab at a dose level of 0.3 mg or 0.5 mg; subjects were masked to these dose levels. Treatment was administered monthly for three initial doses (Day 0, Month 1, and Month 2), with scheduled follow-up visits on Months 3,6,9, and 12. Retreatment after the first three injections was performed as needed, on the basis of predefined criteria with injections no more frequently than every 30 days.

Cohort 2 (N=1992) consisted of subjects enrolled after the majority of Cohort 1 subjects had been enrolled, with enrollment continuing until ranibizumab was approved or denied by the FDA for US marketing, and if approved, until commercially available or 30 September 2006, whichever was earlier. Subjects in Cohort 2 received open-label ranibizumab at the 0.5 mg dose level, with an initial injection on Day 0 followed by retreatment at the physician's discretion, no more frequently than every 30 days. Subjects were monitored for safety for a total of 12 months; safety information, including both serious and nonserious adverse events, was collected at every clinic visit, with two formal safety visits scheduled at Months 6 and 12.

The study consisted of a 30-day screening period and a 1-year treatment period. Treatment duration was approximately 197 days for both dose groups in Cohort 1 and 144 days for subjects in Cohort 2. The mean follow-up time differed between Cohort 1 and Cohort 2, 337 days versus 254 days, respectively.

Ranibizumab was well tolerated, and the incidence of ocular SAEs and AEs was low and unrelated to dose. The rates of individual key ocular SAEs in Cohort 1 were < 1% and were similar across dose groups. Endophthalmitis or presumed endophthalmitis developed in 0.2% subjects in the 0.3-mg group and 0.4% subjects in the 0.5-mg group. The incidence of ocular inflammation, including iritis, uveitis, vitritis, and iridocyclitis was 1.9% in the 0.3-mg group and 1.5% in the 0.5-mg group. Overall cataract rates were 5.4% (0.3 mg) and 6.0% (0.5 mg) and were similar when broken down by nuclear, subcapsular, and cortical subtypes. The rates of individual key ocular SAEs in Cohort 2 were <1%.

The rates of key non-ocular SAEs and AEs, including Antiplatelet Trialists' Collaboration (APTC) ATEs, MI, and vascular death were similar for cohorts 1 and 2 and 0.3- and 0.5-mg dose groups. The incidence of MI and non-ocular hemorrhage was similar across Cohort 1 dose groups. APTC ATEs, including vascular and unknown deaths, nonfatal MI, and nonfatal cardiovascular accidents, were similar across dose groups. During the 12-month study period, 0.7% of subjects in the 0.3-mg

group and 1.2% of subjects in the 0.5-mg group suffered a stroke. The number of vascular deaths and deaths due to unknown cause did not differ across dose groups. Rates of key non-ocular SAEs in Cohort 2 were generally lower than those in Cohort 1. Refer to the Ranibizumab Investigator Brochure or Lucentis® Package Insert for additional details regarding clinical safety experience with ranibizumab.

## **2. OBJECTIVES**

*This Phase I study will investigate the safety and tolerability of intravitreally administered Ranibizumab in three initial monthly doses of 2.0 mg followed by a 9 month period of criteria-based, as-needed retreatment and 12 month off drug safety follow up in subjects with exudative polypoidal choroidal vasculopathy (PCV) for a total of 24 months.*

### **2.1 Primary Objective**

To investigate the safety and tolerability of 3 initial intravitreally administered injections of 2.0 mg Ranibizumab with a 9 month PRN treatment period and 12 month off drug safety follow up.

### **2.2 Secondary Objectives**

- 1. To investigate the changes from baseline in best corrected visual acuity (BCVA) at specified time points in subjects treated with 2.0mg intravitreal Ranibizumab.*
- 2. To investigate the occurrence of ocular non-serious and serious adverse events through fluorescein and ICG angiography, fundus photography, spectral domain optical coherence tomography (OCT) at specified time points.*
- 3. To investigate the occurrence of ocular non-serious and serious adverse events through direct and indirect ophthalmic examinations at specified time points.*

## **3. STUDY DESIGN**

### **3.1 DESCRIPTION OF THE STUDY**

**Design-**

Phase I Safety Study, Open-Label, Single-Center, Non-Randomized, Uncontrolled, Consecutive Case-Series.

### **Population and Sample-**

Random sample of 20 consecutive adults, age >18 years, with polypoidal choroidal vasculopathy. Polypoidal choroidal vasculopathy (PCV) will be defined as CNV with occult characteristics on fluorescein angiography with saccular dilations and polypoidal interconnecting vascular channels on indocyanine green angiography and/or fluorescein angiography. PCV may be defined as a distinct clinical syndrome if the aneurysmal dilatations are visible clinically as reddish-orange and/or there are multiple hemorrhagic PED's. There may be some overlap with AMD in elderly patients. Elderly PCV patients may demonstrate drusen; however PCV may be defined in elderly patients when CNV is observed in peripapillary region, when drusen are not prominent, and when the patient is non-white, especially in African Americans (the likely major racial predilection for PCV in our patient population).

### **2.0 mg Ranibizumab cohort**

Twenty eyes will be treated; PCV eyes may be treatment naïve or received previous PCV therapy greater than 30 days prior to enrollment. A maximum of 10 eyes that completed 24 month enrollment in our study evaluating 0.3 mg or 0.5mg Ranibizumab may be included. *Eyes will be treated with 3 monthly doses of 2.0 mg ranibizumab followed by 2.0mg ranibizumab on a PRN dosing regimen for 9 months.*

*In the year 2 off drug treatment period subjects will be contacted via telephone interview for review of adverse events at month 18 and month 24.*

### **Trial Schema-**

Consented, enrolled patients will receive 3 consecutive monthly intravitreal 2.0 mg/0.5 ml Ranibizumab injections *with the first injection occurring at Day 0 and*

*second and third injection occurring at month 1 and 2 respectively. The first injection will be followed by a 1wk post treatment safety assessment.*

*During the 3rd through 12th month, evaluations for retreatment will occur monthly (every 28-30 days). Retreatment with intravitreal 2.0 mg Ranibizumab or other therapies will be at the investigators discretion but guidelines for recommended retreatment are as follows:*

*Retreatment with 2.0 mg Ranibizumab is recommended if any of the following criteria are met:*

- 1. There is a  $\geq 5$  letter visual acuity loss from the previous visit if associated with disease activity on OCT (intraretinal edema, subretinal fluid, pigment epithelial detachment with fluid etc).*
- 2. There is a  $\geq 50$  um increase in OCT CSF thickness from the previous visit.*
- 3. There is persistent disease acitivity on OCT (intraretinal edema, subretinal fluid, pigment epithelial detachment with fluid etc).*

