#### **4.3 STUDY TREATMENT**

##### **4.3.1 Formulation**

Ranibizumab 2.0mg is formulated as a sterile solution aseptically filled in a sterile 3-mL stoppered glass vial. Each vial contains 0.5 mL of 40 mg/mL (2.0mg dose level) ranibizumab aqueous solution (pH 5.5) with 10 mM histidine HCl, 10% trehalose

dihydrate, and 0.01% polysorbate 20, pH 5.5. The vial contains no preservative and is suitable for single use only. Vials should be protected from direct light.

For further details and molecule characterization, see the Investigator Brochure.

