#### **4.3.2 Dosage, Administration, and Storage**

**1. Dosage-** 2.0 mg/0.05 ml Ranibizumab will be given monthly *from Day 0 through Month 2*, and then at the discretion of investigator no more frequent than monthly for months 3-12.

**2. Administration-** Intravitreal Injection *will only be given* at the Southeast Retina Center *location*.

\*See Appendix B for detailed pre-injection procedures.

**3. Storage-** Upon receipt, study drug kits will be refrigerated at 2°C - 8°C (36°F - 46°F). Vials will not be used beyond the expiration date. Ranibizumab vials will remain refrigerated and will not be frozen.

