#### **4.4 CONCOMITANT AND EXCLUDED THERAPIES**

Starting at month three (ranibizumab injection #1 at baseline, #2 at month 1, and #3 at month 2), treatment will occur at the discretion of the investigator. Observation is permitted as well as intravitreal 2.0 mg Ranibizumab as frequent as every month for months 3-12. Other anti-VEGF agents, such as Avastin or Macugen® or 0.5mg Ranibizumab, will not be permitted. At the discretion of the investigator, *starting* at month 3 thermal laser, photodynamic therapy with Visudyne®, intravitreal or periocular steroids are permitted, if necessary.

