## APPENDIX C

### Preparation and Administration of Ranibizumab Injection

The injecting physician will prepare the ranibizumab injection as outlined below.

Vials of ranibizumab in aqueous solution should remain refrigerated at 2°C–8°C (36°F–46°F) until just prior to use. DO NOT FREEZE vials. Protect from direct light. Do not use beyond the expiration date. Dose solutions should be prepared immediately before dosing. Dose solutions are for single use only.

After preparing the study eye as outlined in Appendix B, withdraw 0.2-mL ranibizumab dose solution through a 5-µm filter needle. Remove the filter needle, replace it with a 30-gauge, 1/2-inch Precision Glide® needle, and **expel excess ranibizumab so that the syringe contains 0.05 mL of solution**. Insert the syringe through an area 3.5 to 4.0 mm posterior to the limbus, avoiding the horizontal meridian, and aiming toward the center of the globe. **The injection volume should be delivered slowly**. The needle should then be removed slowly to ensure that all drug solution is in the eye. **The scleral site for subsequent intravitreal injections should be rotated**. Refer to Appendix D for detailed post-injection procedures.

All injection materials (i.e., syringes, needles) will be discarded in a sharps container immediately following each ranibizumab injection. The ranibizumab drug kit (including the used vial) will be sealed by the injecting physician or technician with the “Do Not Tamper” seal provided in the drug kit.

A patient's study eye will be monitored with a finger count test within 15 minutes of the ranibizumab injection by the physician. A measurement of IOP in the study eye will be obtained 30 ( $\pm 5$ ) minutes post-injection. If the IOP is increased  $\geq 10$  mmHg compared with the pre-injection IOP, then measure the IOP again at 60 ( $\pm 10$ ) minutes. The following table provides specific instructions for the preparation and administration ranibizumab in aqueous solution.

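### The Trial Schema prints the 2.0 mg dose volume as 0.5 ml instead of 0.05 ml, and the text allows a Month 12 injection that the flowchart does not, with no scheduled eye examination afterwards

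*Combined protocol and SAP*

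**What the plan says.** **Dose volume.** The Trial Schema in Section 3.1 says: "Consented, enrolled patients will receive 3 consecutive monthly intravitreal 2.0 mg/0.5 ml Ranibizumab injections". The other places that bear on volume are:

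- Section 4.3.1: "Each vial contains 0.5 mL of 40 mg/mL (2.0mg dose level) ranibizumab aqueous solution".
- Section 4.3.2: "2.0 mg/0.05 ml Ranibizumab will be given monthly".
- Appendix C (preparation and administration): the physician is to "withdraw 0.2-mL ranibizumab dose solution through a" filter needle, and then "expel excess ranibizumab so that the syringe contains 0.05 mL of solution".

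**Last injection visit.** After the three initial doses, Section 4.3.2 allows ranibizumab "and then at the discretion of investigator no more frequent than monthly for months 3-12", and Section 4.4 says: "Observation is permitted as well as intravitreal 2.0 mg Ranibizumab as frequent as every month for months 3-12". Section 3.1 schedules retreatment evaluations up to the 12th month and places optional injection under its Month 3-12 heading. In Appendix A the injection row is blank at Month 12, and note a limits the optional injections to months 3-11.

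**Follow-up after an injection.** On the injection day, Appendix C says the study eye "will be monitored with a finger count test within 15 minutes of the ranibizumab injection". IOP is measured at about 30 minutes and repeated at about 60 minutes if it has risen by 10 mmHg or more. The one-week safety visit follows the first dose only (Section 3.1, Appendix A). The 7-day contact (Section 5.1) and the 30-day (±7) evaluation (Section 4.5.2) are for subjects who leave early. After Month 12 the only scheduled contacts are telephone interviews at Months 18 and 24.

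**The concern.** The Trial Schema is one of the places a reader looks for the dose, and the aim of this Phase I study is the safety of a raised dose. A tenfold volume error should not stand there. The wrong figure also equals the true vial fill of 0.5 mL, so it does not look odd on a quick reading.

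The Month 12 conflict matters because of what would follow such an injection. Section 3.3.1 names endophthalmitis, retinal detachment and uveitis among the primary safety events. Finger counting and IOP on the day would not be expected to detect events that appear days later. After every other injection, a clinic examination within about a month provides a second chance. After a Month 12 injection there is none, so detection would rest on the subject reporting symptoms or on a telephone call six months later. The dose would also fall at the very end of the Day 0 to Month 12 adverse event window in Section 5.1.

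**Working it through.** **1. Volume**

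Inputs: dose 2.0 mg (Sections 3.1 and 4.3.2); concentration 40 mg/mL and vial fill 0.5 mL (Section 4.3.1); volume drawn 0.2 mL and volume injected 0.05 mL (Appendix C).

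- The plan's schema figure: implied concentration = dose / volume = 2.0 / 0.5 = 4 mg/mL. No such strength is described, so the figure cannot be reproduced.
- Required volume = dose / concentration = 2.0 / 40 = 0.05 mL, which agrees with Section 4.3.2 and Appendix C.
- Dose in the schema volume = 0.5 × 40 = 20 mg. This is the whole vial content, and 20 / 2.0 = 10 times the intended dose.
- Most that is ever in the syringe under Appendix C = 0.2 × 40 = 8 mg, before expelling to 0.05 × 40 = 2.0 mg. A 20 mg dose therefore cannot be reached if that procedure is followed.

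**2. Number of injections**

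The three initial doses are at Day 0, Month 1 and Month 2.

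| Source | Optional visits | Maximum injections per eye |
|---|---|---|
| Sections 4.3.2 and 4.4 (months 3-12) | 10 | 3 + 10 = 13 |
| Appendix A (months 3-11) | 9 | 3 + 9 = 12 |

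The nine-month as-needed period in Section 2 and Section 3.1 does not decide between them. Months 3 to 11 are nine visits, but Month 3 to Month 12 is also nine elapsed months, and 3 + 9 + 12 = 24 months fits either reading. The bar on 2.0 mg ranibizumab in Section 3.1 appears under Months 18 and 24 and does not expressly cover the Month 12 visit.

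**3. Next scheduled contact after each injection**

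| Injection at | Next scheduled contact |
|---|---|
| Day 0 | Clinic at 1 week, then Month 1 |
| Months 1 to 11 | Clinic visit about 28-30 days later |
| Month 12 | Telephone at Month 18 |

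Month 12 to Month 18 is 6 months, about 180 days. Relative to the usual interval this is 180/30 = 6.0 to 180/28 = 6.4 times as long, and the contact is a call, not an examination. A subject who withdraws early is contacted at 7 days and examined at about 30 days. A completer injected at Month 12 would get neither.

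**The case against.** The strongest reply on the volume is that nobody would be misdosed. The milligram dose is correct even in the faulty sentence, the section headed Dosage has the right volume, and the physician works from the Appendix C steps. That stands, and it makes this a text error, not evidence of a planned 20 mg dose. It does not make the sentence right.

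On Month 12, Appendix A is the visit-by-visit schedule, and its nine optional visits fit the stated nine-month period neatly. A Month 12 dose would also fall on the day the off-drug year begins. This favours Month 11 as the intended last visit, but two numbered sections say month 12 in plain words, and an investigator could follow either.

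The adverse event window is also less abrupt than one line of Section 5.1 suggests. The same section defines the on-study period as running to the last study visit, and Appendix A marks adverse event review at Months 18 and 24. Later events would therefore be collected, but late and without an eye examination.

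Finally, early events after the second and later injections already depend on the subject reporting them, because the one-week visit follows the first dose only. That is true. What a Month 12 injection loses is specifically the one-month examination. The two items also have different causes and remedies, and each should be judged separately.

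**Conclusion.** Both points hold.

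The schema volume is ten times too large at the only concentration the protocol describes. The practical risk is small provided Appendix C is followed, but the dosing sentence is wrong as written and should be corrected.

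The documents contradict each other on whether a Month 12 injection is allowed. The difference is at most one optional injection per eye (13 against 12). Its consequence is a gap of about 180 days, instead of a clinic visit at 28-30 days, with no scheduled examination for events named in the primary outcome. How many subjects this would touch depends on how many are retreated at Month 12. The documents do not say, so the range is 0 to 20.

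The gap applies to subjects who stay in the study after Month 12, and the 180 days assumes 30-day months. Neither point bears on sample size or on the analysis.

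**What to change.** 1. In the Trial Schema (Section 3.1), change 0.5 ml to 0.05 ml. Section 4.3.1 needs no change, since its 0.5 mL is the vial fill.
2. Amend Sections 3.1, 4.3.2 and 4.4 so that Month 11 is the last ranibizumab injection visit, as in Appendix A. The Month 12 visit then serves as the examination after the last possible injection.
3. If Month 12 injections are intended, correct Appendix A instead. Extend to those subjects the 7-day contact of Section 5.1 and the 30-day (±7) evaluation of Section 4.5.2, and state that adverse events are collected through that evaluation.

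The cost is a wording amendment. Under the Month 11 rule each eye loses at most one optional injection. Under the alternative, each subject injected at Month 12 needs one extra contact and one extra visit.

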**1wk post treatment safety visit following intravitreal injection of Ranibizumab injection:**

Snellen visual acuity with spectacles or pinhole, intraocular pressure, dilated slit lamp examination with biomicroscopy and indirect ophthalmoscopy, and blood pressure.

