**Month(s) 3 -12:**

Blood Pressure, Manifest Refraction, ETDRS Best Corrected Visual Acuity, IOP, dilated slit lamp examination with biomicroscopy and direct ophthalmologic exam, Fluorescein/ICG Angiography (mandatory at months 3,6,9,12; optional at other visits), OCT, and Fundus Photography (mandatory at months 3,6,9,12; optional at other visits). Urine pregnancy test at month 12 for females of childbearing potential only.

*From months 3 onward, at the discretion of the Investigator, Intravitreal 2.0 mg Ranibizumab, observation or non-study therapy (i.e. laser, intravitreal steroids, PDT etc.) may be administered. Other anti-VEGF agents including bevacizumab and standard dose (0.5mg) ranibizumab are excluded as optional therapies.*

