### 4.8.3 Efficacy Analyses

1. **Primary Endpoint-** See Section 3.3.1

2. **Secondary Endpoints-** See Section 3.3.2

All subjects will be used in analysis of primary and secondary outcome parameters. Rates for the endpoints at the suggested time points will be presented as a % of the patients enrolled. Analysis of Variance will be used to assess for role of variables in for the endpoints. Variables will include # Ranibizumab injections, other therapies, baseline acuity, age, gender, etc.

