### **5.1 ADVERSE EVENTS**

*All adverse events occurring from Day 0 through Month 12 or Early Withdrawal will be documented and assessed by the principal investigator.* Subjects discontinuing early from the study should return for an early termination evaluation and will be contacted 7 days after their last injection or study visit to elicit for occurrence of adverse events (serious and nonserious).

For this protocol, an AE is any “on study” untoward medical occurrence (e.g., sign, symptom, disease, syndrome, intercurrent illness) that occurs in a study subject, regardless of the suspected cause. “On study” refers to Day 0 through the last study visit.

Unchanged, chronic conditions are NOT AEs and will not be recorded. An exacerbation or worsening of a chronic condition should be recorded as an AE.

Both serious and nonserious AEs should be graded on a three-point scale (mild, moderate, severe) and reported in detail in the subjects clinic record.

The suggested definitions are as follows:

Mild: Discomfort noticed but no disruption of normal daily activity

Moderate: Discomfort sufficient to reduce or affect normal daily activity

Severe: Incapacitating with inability to work or perform normal daily activity

Using the following criteria, the investigator will also assess whether there is a reasonable possibility that study drug caused or contributed to the AE.

- Yes (possibly or probably)

There is a clinically plausible time sequence between onset of the AE and study drug administration; and/or

There is a biologically plausible mechanism for study drug causing or contributing to the AE; and

- No

The AE may or may not be attributed to concurrent/underlying illness, other drugs, or procedures.

A clinically plausible temporal sequence is inconsistent with the onset of the AE and study drug administration; and/or

A causal relationship is considered biologically implausible.

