**APPENDIX A**  
**Study Flowchart**

	Screen	Baseline (Day 0)	1 wk Safety Follow-up c after first dose only	Month 1	Month 2	Months 3 – 11	Month 12	Month 18 & 24
Informed consent	X							
Demographics	X							
Physical Examination and Medical History	X							
Vitals	X	X	X	X	X	X	X	
Urine Pregnancy Testing	X						X	
Ocular Exam b	X		X	X	X	X	X	
OCT SD	X	X		X	X	X	X	
FA/ICG	X	X		X	X	Xf	Xf	
Fundus photos	X	X		X	X	Xf	Xf	
Ranibizumab Injection		X		X	X	(X) a		
AE and ConMed Review		X	X	X	X	X	X	X
ETDRS Refraction & Visual Acuity (4 m) e	X	X	X	X	X	X	X	

Note:

a Ranibizumab injections for months 3-11, to be determined based on investigator's discretion.

b Ocular Exam includes IOP. Study eye only at safety assessments

c Safety Assessment post Injection to be performed 1 week after ranibizumab injection

e Refraction not required at 1 wk safety follow-up.

f F/A/ICG/photos performed at months 3,6,9 and 12 but may be performed monthly at investigator discretion

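### The 1-week examination follows injection 1 only, so short-lived findings seen only on examination are under-recorded after later injections, and their relation to injection count is understated

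*Combined protocol and SAP*

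**What the plan says.** Section 3.1 (Trial Schema) ties the early visit to one injection: "The first injection will be followed by a 1wk post treatment safety assessment". The matching column of the Appendix A flowchart is marked "after first dose only". Footnote c, attached to that column, reads "Safety Assessment post Injection to be performed 1 week after ranibizumab injection"; neither it nor the heading of the visit in Section 3.1 repeats the limit. The visit is a real examination: acuity, intraocular pressure (IOP), "dilated slit lamp examination with biomicroscopy and indirect ophthalmoscopy, and blood pressure".

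After later injections the next scheduled dilated examination is the monthly visit, which has "IOP, dilated slit lamp examination with biomicroscopy and direct ophthalmologic exam". For the as-needed period Section 3.1 says "evaluations for retreatment will occur monthly (every 28-30 days".

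Other monitoring is not limited to injection 1. Appendix C requires a finger-count test within 15 minutes and an IOP reading at 30 minutes, repeated at 60 minutes after a rise of 10 mmHg or more. The flowchart has adverse-event review at every visit from Day 0. Section 5.1 adds a 7-day contact, but only for subjects who leave early: they "will be contacted 7 days after their last injection or study visit to elicit for occurrence of adverse events".

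Section 3.3.1 names drug- or procedure-related uveitis among its examples of the primary outcome. Section 4.8.3 covers primary and secondary outcomes, gives rates as a percentage of patients enrolled, and plans an ANOVA: "Variables will include # Ranibizumab injections, other therapies, baseline acuity, age, gender, etc". Section 4.8.2 summarizes safety with no reference to injection number.

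**The concern.** This is a Phase I safety study of repeated 2.0 mg dosing, so whether findings accumulate with further injections is a central question. An eye with 3 injections and an eye with 12 each get exactly one early examination. For findings that come and go between monthly visits, most of what injections 2 onward cause is not looked for at the time it is present, yet the planned analysis relates events to injection count as if the search were equally thorough throughout.

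The rule in Section 4.8.4 (available cases, no imputation) does not help, because an examination that was never scheduled is not a missing value. The risk is that fewer mild inflammatory findings after the first injection, or a flat relation to injection count, are read as good tolerance of repeat dosing when the examination schedule alone could produce them.

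**Working it through.** The plan states no event rate, power or maximum number of injections, so there is no figure to reproduce.

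**Step 1: how many injections get the early examination.** The sample size is 20 (Section 4.8.1). The maximum depends on whether month 12 is an injection visit. Appendix A (months 3-11) and the 9-month period in Section 2 give 3 + 9 = 12. Sections 4.3.2 and 4.4 (months 3-12) give 3 + 10 = 13.

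- Minimum, 3 per subject: 20 of 60 = 33%.
- Maximum 12: 20 of 240 = 8.3%.
- Maximum 13: 20 of 260 = 7.7%.

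**Step 2: detection model.** The durations and reporting shares are assumptions; the documents give neither. Each injection causes a transient finding with probability λ, starting at the injection and lasting an exponential time with mean τ days. A share s is reported by the subject whatever the schedule. Examinations fall on days 7 and 28 after injection 1, and on day 28 only after later injections. A finding still present on day 28 was also present on day 7, so:

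- detection after injection 1: d1 = 1 − (1 − s)(1 − exp(−7/τ))
- detection after later injections: d2 = 1 − (1 − s)(1 − exp(−28/τ))
- expected recorded events in an eye with n injections: λ[d1 + (n − 1)d2]

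The recorded slope per extra injection is λ·d2. With a 1-week examination after every injection it would be λ·d1. The attenuation is d2/d1.

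**Step 3: results for d2/d1.**

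| Share reported, s | τ = 7 days | τ = 14 days | τ = 28 days |
|---|---|---|---|
| 0 | 0.018/0.368 = 0.05 | 0.135/0.607 = 0.22 | 0.368/0.779 = 0.47 |
| 0.5 | 0.509/0.684 = 0.74 | 0.568/0.803 = 0.71 | 0.684/0.889 = 0.77 |
| 0.9 | 0.902/0.937 = 0.96 | 0.914/0.961 = 0.95 | 0.937/0.978 = 0.96 |

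At s = 1 the ratio is 1. For a persistent finding (τ = 90 days, s = 0) it is 0.733/0.925 = 0.79. A 30-day interval lowers the first row a little: exp(−23/τ) gives 0.04, 0.19 and 0.44.

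**Step 4: an opposing bias.** Section 3.1 recommends retreatment on signs of disease activity, so more active eyes receive more injections. Assume λ = 0.02, 12 injections in active eyes and 5 in quiet eyes, τ = 14 and s = 0.5. If active eyes have x extra recorded disease-related events each, the recorded slope relative to equal ascertainment is [d2 + x/(0.02 × 7)]/d1:

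- x = 0: 0.71
- x = 0.05: 1.15
- x = 0.10: 1.60
- x = 0.20: 2.49

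So the direction for the pooled primary endpoint is not fixed, even though it is for transient examination-only findings taken alone.

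**The case against.** The strongest reply is that the eye is monitored after every injection. The finger-count and IOP checks apply each time, and Section 1.5 places IOP increases within 60 minutes of injection, which is the window those checks cover. Monthly visits repeat IOP, blood pressure and a dilated examination, and subject reports count toward the primary outcome. All of this stands. It confines the point to findings that are short-lived and unnoticed by the subject.

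The second reply is that little will be lost. Section 1.5 reports ocular inflammation in 1.5% to 1.9% of subjects over 12 months at lower doses in a different disease. That would be 20 × 0.015 = 0.30 to 20 × 0.019 = 0.38 subjects here. This also stands: the split rows will be sparse. But an ANOVA on injection count would be no more informative with so few events, and it would carry the bias as well.

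Three stronger readings are tempting, and the documents do not support them.

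- A reader might infer that every relation of events to injection count is biased downward. Endophthalmitis, retinal detachment or a 30-letter loss would usually persist or be noticed, and Step 4 shows a pull the other way.
- A reader might infer that recorded events become rarer with more injections by construction. At constant risk the expected count per eye rises by λ·d2 with each injection, which cannot be negative. Only a rate per injection would fall, and Section 4.8.3 plans percentages of patients.
- A reader might take footnote c to require a 1-week visit after every injection. It hangs on a column limited to the first dose, and the Trial Schema is explicit. This is a matter of tidying the wording.

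**Conclusion.** The point holds for one class of event: transient findings detected only by examination. For these, ascertainment differs between injection 1 and later injections, and the relation to number of injections is understated. The recorded slope is roughly one twentieth to one half of its equal-ascertainment value if subjects report none of the episodes, about three quarters if they report half, and nearly intact if they report 90%. These sizes rest on constant risk per injection, onset at the injection, exponential duration with a mean of 1-4 weeks, and the assumed reporting shares. The direction for this class needs only that some episodes are present at 1 week, have ended by the monthly visit, and are not otherwise reported.

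The effect on the whole primary endpoint depends on the mix of events and cannot be stated. This is an inexpensive correction to the analysis section. It does not show that the safety monitoring is inadequate.

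**What to change.** In Sections 4.8.2 and 4.8.3:

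1. Tabulate examination-detected transient findings separately for injection 1, split into those found at the 1-week visit and those found at the monthly visit, and for injections 2 onward (monthly visit only). Give the number of injections and the examination interval for each row. Count a finding still present at the monthly visit in that row even if it was already seen at 1 week; otherwise the like-for-like comparison between first and later injections is lost.
2. Keep same-day IOP rise outside this split, since it is checked after every injection.
3. Do not use number of injections as an ANOVA variable for these findings.
4. State that a lower recorded rate after later injections is not evidence of tolerance.

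Two points need reconciling before such a table can be built. Appendix A and the 9-month period in Section 2 conflict with Sections 4.3.2 and 4.4 on whether month 12 is an injection visit. This decides whether the maximum is 12 or 13, and an injection at month 12 would have no later scheduled examination, because months 18 and 24 are telephone interviews. Footnote c and the 1-week visit heading should also carry the same first-dose limit as the Trial Schema and the flowchart column.

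The cost is analysis wording and one table split of data already collected, with no added visit. The downside is small counts in each row.
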